8.8.2. Adverse Events

AEs will be coded to the preferred terms of the Medical Dictionary for Regulatory Activities (MedDRA®). Summaries will present by system organ class (SOC), preferred term (PT), and severity (mild, moderate, severe) the number and percentage of subjects for whom events were reported.

In general, a treatment-emergent adverse event (TEAE) will be defined as any AE that begins on or after the date and time of the first dose of study drug and up to the date of last dose of study drug plus the number of days in the follow-up period.

TEAEs will be summarized separately for the Induction and ATE phases. Assignment of TEAEs to different phases of the study (Induction or ATE) will be detailed in the SAPs.

All AEs will be listed by subject. The number and percentage of subjects who experience TEAEs will be summarized. Summaries of TEAEs will include the following types of summaries:

- All AEs, by SOC and PT and also by PT (by descending overall frequency)
- All AEs, by SOC, PT, and severity
- All study drug-related AEs, by SOC and PT
- All study drug-related AEs, by SOC, PT, and severity
- All AEs leading to premature discontinuation of study drug, by SOC and PT
- All AEs leading to temporary interruption of study drug, by SOC and PT
- All SAEs, by SOC and PT
- All study drug-related SAEs, by SOC and PT

A listing will be provided for all subjects who experience an SAE. Listings will also be provided for subjects who discontinued study treatment prematurely because of AEs and subjects who temporarily interrupted study treatment because of AEs. AEs of Special Interest, as described in Section 7.1.4, will be listed and summarized.

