3.7.2. Adverse Events

Adverse events (AEs) will be coded to the preferred terms (PT) of the Medical Dictionary for Regulatory Activities (MedDRA®). Summaries for induction period and for the complete study period will be presented separately and by system organ class (SOC), preferred term, and severity and/or relatedness, the number and percentage of subjects for whom events were reported.

Adverse events (AEs) are recorded from signing of the informed consent form through the final follow-up assessment. Adverse events observed prior to first dose are non-treatment emergent.

All summaries will be presented for both the Induction Period and the overall study period separately.

Treatment emergent adverse events are defined as follows for induction period and overall:

- Induction period TEAEs are events with a start date/time after the first dose date/time in Induction period up to the date/time of ATE Day 1 dose or date of last dose of study drug + 28 days, whichever is earlier.
- TEAEs for the whole study and listings are defined as AEs with onset on or after the first initiation of study drug up to the date of last dose study drug + 28 days.

Only treatment-emergent AEs will be summarized in the tables. Separate by-subject listings of all TEAEs and all non-TEAEs will be provided.

An AE will be considered a treatment-emergent serious AE (TESAE) if it is a TEAE that additionally meets any SAE criteria.

If more than 1 AE is coded to the same preferred term for the same subject, the subject will be counted only once for that preferred term using the most severe and most related occurrence for the summarizations by severity and by relationship to study drug.

Summary tables will also be provided for Induction period and overall for subjects with:

- TESAEs by SOC and PT
- TEAEs leading to discontinuation of study drug by SOC and PT
- Drug related TEAEs by SOC and PT
- TEAEs by severity and by SOC and PT
- TEAEs resulting in death by PT

Listings of all AEs, SAEs, and AEs leading to premature study drug discontinuation by subject will be presented.

An overall summary of adverse events will also be presented and will include the following summary lines: Any AE, Moderate or Severe AEs, AEs Related to Study Drug, Moderate or Severe AEs Related to Study Drug, Serious AEs, Serious AEs Related to Study Drug, AEs Leading to Premature Study Drug Discontinuation, AEs Leading to Temporary Interruption of Study Drug, and Deaths During Study.

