5.3.2. Missing Date Imputation

5.3.2.1. Missing/Incomplete AE/Start Date

Imputation of dates with missing day and/or month is only applied to TEAEs. TEAE start dates with missing day or month will be imputed as follows:

- If day and month are missing but year is available, then the imputed day and month will be 01 Jan or the initial treatment date if they have the same year, whichever is later (because TEAE onset is not expected prior to administration of study treatment)
- If day is missing but the month and year are available, then the imputed day will be the first day of the month or the initial dosing date if they have the same month and year, whichever is later.

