5.4. Adverse Event Start and End Date/Time Imputation Rules

Missing start date and times will be handled as follows:

- AE onset date completely missing:
 - If AE is not ongoing and AE onset date missing and AE end date missing, then impute AE onset as date/time of first dose.
 - Else if AE is not ongoing and AE onset date missing and AE end date not missing and date/time of first dose <= AE end date, then impute AE onset as date/time of first dose of study drug.
 - Else if AE is not ongoing and AE onset date missing and AE end date not missing and AE end date is BEFORE first dose of study drug, then impute AE onset as AE end date YEAR and MONTH with 01 as the day and 00:00 as time.

- Else if AE IS ongoing and AE onset date missing, then impute AE onset as date/time of first study drug dose.
- AE onset date has year and month only:
 - If AE onset date has year and month only and they are the year and month of first dose of study drug, then impute AE onset as date/time of first dose:
 - Else if AE onset date has year and month only and date/time of first dose is not missing, then impute AE onset as AE onset year and month with 01 as the date and 00:00 as the time.
- AE onset date has year only:
 - If AE onset date has year only and it is year of first dose of study drug, then impute AE onset as date/time of first dose of study drug.
 - Else if AE onset date has year only and date of first study drug dose is not missing and year of AE onset is NOT the year of first dose of study drug, then impute AE onset as Jan. 1 of the AE onset year and 00:00 as the time.
- AE onset missing (where it was not handled by the above cases):
 - If AE onset date is missing, then impute AE onset as date/time of first study drug dose.
- AE onset has complete date but missing time:
 - If AE onset date is a date only and is same as date of first study drug dose, then impute AE onset as date/time of first study drug dose:
 - Else if AE onset date is a date only and is NOT = date of first study drug dose, then impute AE onset as AE onset date with 00:00 as the time:

Missing end date and times will be handled as follows:

- AE end date - completely missing:
 - If AE if not ongoing and both AE onset and AE end dates are missing, then impute AE end date as date/time of last study drug dose.
 - Else if AE is not ongoing and AE onset date not missing and AE end date missing AND AE onset date <= date/time of last dose, then impute AE end date as date/time of last study drug dose.

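### SAP 3.7.2 opens the Induction TEAE window strictly after first dose, so AEs that SAP 5.4 imputes to the moment of first dose would, read literally, miss the Induction tables

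*SAP*

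**What the plan says.** SAP 3.7.2 gives two different lower bounds in adjacent bullets. For Induction: "Induction period TEAEs are events with a start date/time after the first dose date/time in Induction period". For the whole study: "TEAEs for the whole study and listings are defined as AEs with onset on or after the first initiation of study drug". Just above them it states: "Adverse events observed prior to first dose are non-treatment emergent". Protocol 8.8.2 defines a TEAE as "any AE that begins on or after the date and time of the first dose of study drug". SAP 3.7.2 also limits the AE summary tables to treatment-emergent events.

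SAP 5.4 then places several kinds of AE exactly on that boundary:

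- The rule that begins "If AE onset date is a date only and is same as date of first study drug dose" sets onset to the date and time of that dose.
- The rule that begins "If AE onset date has year only and it is year of first dose of study drug" does the same, and so does the rule for an onset known only to the year and month of first dose.
- A fully missing onset is also set to first dose unless the AE is known to have ended earlier. A catch-all covers a missing onset "where it was not handled by the above cases".

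SAP 5.3.2.1, which also treats partial start dates, says: "Imputation of dates with missing day and/or month is only applied to TEAEs".

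**The concern.** The Induction definition excludes equality and the imputation rules produce it. An AE imputed to first dose then falls between the definitions. It is not pre-treatment, because only AEs before first dose are called non-treatment-emergent. It lies on Study Day 1 (SAP 5.3.1.1) and inside the Induction period, which SAP 3.1.5.1 starts at first dose. Yet it is not an Induction TEAE.

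Induction is the only phase with a placebo group. The whole-study tables cannot stand in for it, because placebo subjects take TD-1473 80 mg in the ATE (Protocol 3.1, Table 2). The exclusion also carries into the dependent Induction tables: in SAP 3.7.2 a treatment-emergent SAE must first be a TEAE, and the tables by relatedness, severity and discontinuation use the same events.

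**Working it through.** The plan states no figure to reproduce here. The check is to apply the SAP 5.4 onset rules and then test each result against the definitions.

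**Rule count.** SAP 5.4 has 11 onset rules. Seven set onset to first dose:

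1. onset and end both missing, AE not ongoing
2. onset missing, end on or after first dose
3. onset missing, AE ongoing
4. the catch-all
5. year only, equal to the year of first dose
6. year and month only, equal to those of first dose
7. a complete date equal to the first-dose date, with no time

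The other four place onset elsewhere: end before first dose, another year and month, another year, and another untimed date (7 + 4 = 11). The catch-all largely repeats the other fully-missing rules, which leaves six distinct patterns.

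**Test.** For illustration, assume first dose at 09:00 on 14 September 2020 and ATE Day 1 dosing 87 days later.

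| Onset as recorded | Imputed onset | Induction, *after* | Induction, *on or after* | Whole study |
|---|---|---|---|---|
| Day 1, no time | first dose | no | yes | yes |
| Month of first dose only | first dose | no | yes | yes |
| Year of first dose only | first dose | no | yes | yes |
| Missing, ongoing | first dose | no | yes | yes |
| Missing, not ongoing, no end date | first dose | no | yes | yes |
| Missing, ended after first dose | first dose | no | yes | yes |
| Missing, ended before first dose | 1st of the end month | no | no | no |
| Day 1, timed after dosing | as recorded | yes | yes | yes |
| Day 2, no time | Day 2, 00:00 | yes | yes | yes |
| A later month only | 1st of that month | yes | yes | yes |

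All six patterns set to first dose fail the Induction rule as written and pass the inclusive one. The other rows do not change. An untimed Day 1 AE drops out while an untimed Day 2 AE stays in.

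**A limit on two of the rows.** SAP 5.3.2.1 restricts imputation of a missing day or month to TEAEs. That is circular, because TEAE status depends on the onset date, and it does not say which TEAE definition is meant. For the month-only and year-only patterns, exclusion is therefore one reading and not the only one.

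**Size.** The documents give no number of affected AEs. A table row changes only for a subject with no other Induction TEAE in that row. Assume 0 to 3 such subjects per group at the planned 60/60/40:

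- active group: 0 to 3/60 = 0 to 5.0 points; one subject is 1/60 = 1.7 points
- placebo: 0 to 3/40 = 0 to 7.5 points; one subject is 1/40 = 2.5 points

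Actual group sizes are not given. SAP section 1 records early termination, and SAP Table 5 excludes two sites from all analysis sets.

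**Errors that the inclusive wording admits.** AEs are recorded from consent and Screening lasts up to 35 days, so an AE that truly began before dosing can be set to first dose under any of the seven rules. Rules 1 to 5 could also hold an AE that truly began in the ATE. Rules 6 and 7 could not: the calendar month of first dose ends by Day 31 at the latest, and ATE Day 1 is at least one day after Week 12 (nominal Day 84), so about Day 85. One such placebo subject would add 1/40 = 2.5 points to a placebo row. This can arise at the Week 12 freeze (SAP 3.9), because subjects enrolled earlier are by then in the ATE.

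**The case against.** The strongest reply is that nobody would mistake the intent. The adjacent bullet and Protocol 8.8.2 are inclusive, SAP 3.1.5.1 starts Induction at first dose, and only AEs before first dose are called non-treatment-emergent. SAP 5.3.2.1 moves early partial dates up to first dose on the ground that a treatment-emergent onset should not precede dosing. The affected AEs may also be few. Protocol 7.3 requires an onset date, so fully missing onsets should be rare. The SAP's use of date/time, with a rule for a missing time, suggests that a time field exists, although the documents do not show the CRF. Finally, the events remain in the listings and whole-study tables, and SAP 3.7 plans in general no inferential tests of AE incidence.

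All of this stands, and it makes the weight minor. It does not remove the point: the Induction bullet is the text to be programmed, it gives no rule for ties, and a literal program leaves these AEs out.

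A reader might infer more than the documents support:

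- That most AEs, or all AEs with a missing onset, are affected. Seven of eleven is a count of rules, not of events, and four rules place onset elsewhere.
- That the AEs vanish from the report. The whole-study definition keeps them.
- That the slip favours TD-1473. The rule is the same in every group, and nothing in the documents gives a direction.

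**Conclusion.** The inconsistency is real and minor. As written, SAP 3.7.2 and SAP 5.4 together leave out of the Induction tables any AE whose onset is imputed to first dose, while the whole-study tables keep it, so the two sets would not reconcile. The wording mismatch is certain. Whether any AE would actually be lost is not: the effect is zero if no AE is imputed to first dose or if the programmer follows the evident intent. The ranges of 0 to 5.0 points (active) and 0 to 7.5 points (placebo) rest on the assumed 0 to 3 subjects per group and the planned sample sizes. They show scale and are not estimates. No efficacy result is touched.

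**What to change.** Three short edits:

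1. In the Induction bullet of SAP 3.7.2, replace *after* with *on or after* the first dose date/time. This restores the protocol's lower bound.
2. In SAP 5.3.2.1, replace the restriction to TEAEs with a statement that partial onset dates are imputed before TEAE classification, and align the section with SAP 5.4. Adding the statement beside the present sentence would leave two opposite rules standing.
3. Flag AEs with imputed onset in the AE listing.

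The cost is one phrase, one rewritten sentence with the alignment, and one listing flag. There are two downsides. A true pre-dose AE (an untimed Day 1 AE, or a screening AE whose missing or partial onset is set to first dose) would count as an Induction TEAE; the whole-study definition already accepts this. An AE with fully missing or year-only onset that truly began in the ATE would count in Induction, and for a placebo subject that could raise the placebo rate, so the change is not uniformly conservative. The flag makes both visible. An AE with a recorded pre-dose time stays non-treatment-emergent.

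Three nearby items are separate and minor:

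- SAP 3.1.6: the actual-treatment table, used after misdispensing, has no placebo row, so a mean dose of 0 mg is classed as 80 mg. It needs a placebo row.
- SAP 3.7.3.3: the QTcF plot refers to Week 8. The schedule has an ECG at ATE Week 8 and none at Induction Week 8, so the two must be reconciled and the visit named.
- SAP 3.7.1: exposure ends at drug return for subjects who stop before Week 12 and in the whole-study formula, whereas SAP 3.7.1.1 already uses the date of last dose. One convention should serve both.

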Subjects who prematurely discontinue the study drug due to adverse events (AEs), lack of response, or any other reason besides withdrawal of consent during Induction or ATE will be asked to return for an Early Study Drug Discontinuation visit. This visit will be conducted within 5 days after the last dose of study drug, if possible. Subjects will also return for the EOS visit for collection of safety data and assessment of disease activity 4 weeks after the Early Study Drug Discontinuation visit.

During ATE, subjects should be assessed for clinical benefit. If there is no clinical benefit, as deemed by the investigator, the subject should stop study drug treatment and be withdrawn from the study.

Figure 1: Study Design Schematic

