6. STUDY PROCEDURES

Study procedures will be performed only after written informed consent is obtained. The Screening visits (i.e., Stage 1 and Stage 2) will be performed within 35 days before dosing. One repeat Screening Stage 1 visit is allowed for each subject per the investigator's discretion. No more than one repeat Screening Stage 1 visit or repeat visit-specific procedure/assessment is allowed for each subject, unless prior written approval has been provided by the Sponsor. If the subject does not begin Induction treatment within this 35-day window, Screening evaluation procedures (i.e., Stage 1 and Stage 2) must be repeated. Subjects may be considered for re-screening of both Screening Stage 1 and Screening Stage 2 procedures, depending on the reason for the initial screening failure, per consultation with and approval from the Sponsor.

During the study, every effort should be made to perform study procedures as listed in the Schedule of Study Procedures (Table 1). Assessments will be made and biological samples will be taken in the following recommended order at those study visits at which they coincide: fecal sample collection, adverse event assessment, ECG, vital signs, [REDACTED] clinical laboratory safety samples, [REDACTED] and ileocolonoscopy with biopsies (although ileocolonoscopy should be done within 3 days prior to the Week 12 clinic visit). Study drug administration will be in-clinic on Day 1, Week 4, Week 8, Week 12, ATE Week 16, ATE Week 24, ATE Week 36, and ATE Week 48 after all pre-dose assessments [REDACTED] and procedures have been completed.

Throughout the study, the acceptable window for scheduled assessments is as follows:

- - 3 to + 5 days from the nominal visit date for Week 4, Week 8, ATE Week 4, ATE Week 8, ATE Week 16, ATE Week 24, ATE Week 36, ATE Week 48 and the EOS visits
- -1 to +3 days from the nominal Week 12 clinic visit for the Week 12 ileocolonoscopy with biopsies. The Week 12 ileocolonoscopy and biopsies should be performed on the same day as the Week 12 visit, preferably in the early morning, to permit morning dosing with study drug. However, if not feasible to perform both the ileocolonoscopy and the clinic visit on the same day, the ileocolonoscopy could be performed within 3 days after the Week 12 clinic visit. However, the Week 12 endoscopy must be performed at least 1 day prior to ATE Day 1.
- + 3 days from the nominal visit date for the Week 12 clinic visit

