 - Pregnancy test for females of childbearing potential – If urine b-hCG test is positive, confirmation with serum b-hCG test is required
- Disease Assessments
 - CDAI
 - Abdominal Pain and Total Stool Frequency Scores
 - [REDACTED]
 - [REDACTED]
- Perform drug accountability and review subject's compliance with study drug dosing
- Subject dosing in clinic (in the morning before eating)
- Review concomitant medications
- Adverse event assessment (AEs, SAEs, Adverse Events of Special Interest)
- Study drug dispensation and re-review of subject instructions for dosing
- Review diary completion and compliance; counsel subject as needed

The investigator should consider discontinuation for any subject who has not responded to treatment by ATE Week 16. Subjects who have not shown clinical improvement at ATE Week 16 should complete an Early Study Drug Discontinuation visit and be discontinued from study drug. They will need to return to complete an EOS visit 4 weeks after their last dose.

6.3.11. ATE Week 24

Subjects should be instructed to fast from food and non-clear fluids on the evening prior to the ATE Week 24 visit to ensure a minimum 8-hour fast prior to the fasted blood sample collection.

The following procedures will be performed at the ATE Week 24 visit:

- Tobacco use status
- Vital signs

- Heart rate (HR) and systolic and diastolic blood pressure (BP)
- Respiratory rate
- Body Temperature
- 12-lead ECG
- Physical examination is to be conducted according to local practice
- Fistula drainage assessment (if applicable) to determine the number of fistula and confirm draining is occurring.
- Weight
- Blood collection
 - Hematology
 - Serum chemistry
 - Overnight fasting lipid panel
 - [REDACTED]
 - [REDACTED]
 - [REDACTED]
 - [REDACTED]
- Urine collection
 - Urinalysis
 - Pregnancy test for females of childbearing potential – If urine b-hCG test is positive, confirmation with serum b-hCG test is required
- Fecal collection [may be collected within 3 full days (approximately 72 hours) prior to the visit; however, it is preferable that the stool sample be collected during the first bowel movement in the morning]
 - [REDACTED]
- Disease Assessments
 - CDAI Components
 - Abdominal Pain and Total Stool Frequency Scores
 - [REDACTED]
 - [REDACTED]
- Perform drug accountability and review subject’s compliance with study drug dosing
- Subject dosing in clinic (in the morning before eating)
- Review concomitant medications

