6.3.14. End of Study

An EOS visit will be required for all subjects 4 weeks following their last dose of study drug. Subjects who complete an Early Study Drug Discontinuation visit during Induction or ATE will also be required to return for an EOS visit.

Subjects should be instructed to fast from food and non-clear fluids on the evening prior to the EOS visit to ensure a minimum 8-hour fast prior to the fasted blood sample collection.

The following procedures will be performed at the EOS visit:

- Vital signs
 - Heart rate (HR) and systolic and diastolic blood pressure (BP)
 - Respiratory rate
 - Body Temperature
- 12-lead ECG
- Physical examination is to be conducted according to local practice
- Fistula drainage assessment (if applicable) to determine the number of fistula and confirm draining is occurring.
- Weight
- Blood collection
 - Hematology
 - Serum chemistry
 - Overnight fasting lipid panel
 - [REDACTED]
 - [REDACTED]
- Urine collections
 - Urinalysis
 - Pregnancy test for females of childbearing potential – If urine b-hCG test is positive, confirmation with serum b-hCG test is required

- Disease Assessments
 - CDAI Components
 - Abdominal Pain and Total Stool Frequency Scores
- Review concomitant medications
- Adverse event assessment (AEs, SAEs, Adverse Events of Special Interest)
- Review diary completion and compliance and collect diary from subject

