7.4.2. AE, SAE and AESI Recording

All AEs, regardless of seriousness, severity, or causal relationship to study medication, will be recorded from signing informed consent through the last study visit (or last subject contact in the case of a follow-up telephone call). AEs will be recorded on the AE page of the CRF. SAEs, regardless of relationship to study medication will be recorded from signing informed consent through the last study visit (or last subject contact in the case of a follow-up telephone call). Additionally, investigators may report SAEs assessed as related to study medication through 30 days following the last study visit (or last subject contact in the case of a follow-up telephone call). All SAEs will be recorded on both the SAE Report Form and the AE page of the CRF and should include the following:

Description of event:

- Signs and symptoms due to a common etiology should be reported as a single diagnosis; for example, cough, runny nose, sneezing, sore throat, and head congestion would be reported as "upper respiratory infection".
- A diagnosis or description must be as specific and as complete as possible (e.g., "lower extremity edema" instead of "edema").
- Hospitalization or surgical procedures should not be used as adverse event terms (e.g., if a subject was hospitalized for cholecystectomy due to cholecystitis, the adverse event term should be recorded as cholecystitis, and not as the procedure, cholecystectomy).
- "Death" should not be used as an adverse event term unless the cause of death is unknown. For events with a fatal outcome, the cause of death should be the adverse event term (e.g., if a subject died of an acute myocardial infarction, the adverse event term should be recorded as "Myocardial Infarction" and the event outcome as fatal).

- Relationship to study medication: The Investigator will make an assessment of the causal relationship of the study medication to the AE using the guidelines in Section 7.3.2.
- Severity: The severity of the AE will be assessed using the guidelines in Section 7.3.1.
- Outcome: The outcome of AEs will be recorded.
- Therapeutic measures: Measures taken for the treatment or management of the AEs will be recorded.

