3.1.5.3. Overall Study Period

For analysis and summaries of the overall study period, only data collected for each subject from first dose up until date of last dose + 5 days will be presented.

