3.7.3.2. Vital Signs

Descriptive statistics for vital signs (systolic and diastolic blood pressures, pulse rate, and weight) and changes from baseline values at each visit and at the end of study will be presented by treatment group.

For each nominal time point, vital signs will be summarized in terms of observed values and changes from baseline. Marked abnormalities as defined in Table 8 will be flagged in the listing.

Table 8: Criteria for Marked Abnormalities in Vital Signs

Heart Rate (bpm)	Systolic Blood Pressure (mm Hg)	Diastolic Blood Pressure (mm Hg)
< 40	< 85	< 45
> 110	> 160	> 100

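### The SAP's last dose + 5 days limit keeps the End of Study visit out of the overall safety summaries, against SAP 3.7.3.2 and 3.7.3.3, and the protocol gives that visit two different anchors

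*SAP*

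**What the plan says.** **Data period and windows.** SAP 3.1.5.3 limits overall-period analyses and summaries: "only data collected for each subject from first dose up until date of last dose + 5 days will be presented". SAP 3.1.5.1 and 3.1.5.2 use the same + 5-day end for Induction (unless the ATE Day 1 dose comes first) and for the Active Treatment Extension (ATE). The window table in SAP 3.1.3 runs from Screening to ATE Week 48 (ATE Days 329 to 350) and has no EOS row. Anything outside a window is labelled unscheduled, whatever its nominal label. SAP 3.1 admits only scheduled or windowed visits to summaries unless noted otherwise.

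**Promised displays.** SAP 3.7.3.2 says vital-sign statistics "at each visit and at the end of study will be presented by treatment group". SAP 3.7.3.3 promises ECG statistics at each time point up to the end of study. SAP 3.7.3.1 promises laboratory summaries for Induction and overall, without naming EOS.

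**Adverse events.** Protocol 7.4.2 says AEs "will be recorded from signing informed consent through the last study visit". SAP 3.7.2 counts whole-study TEAEs "up to the date of last dose study drug + 28 days". It puts only TEAEs in the tables and gives non-TEAEs their own listing.

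**Timing of EOS.** Protocol 6.3.14: "An EOS visit will be required for all subjects 4 weeks following their last dose of study drug". The EOS paragraph of Protocol 3.1 and footnote B of the schedule in SAP 1.4 agree. For subjects stopped at ATE Week 16, Protocol 6.3.10 says "They will need to return to complete an EOS visit 4 weeks after their last dose". The early-discontinuation paragraph of Protocol 3.1 instead calls for "assessment of disease activity 4 weeks after the Early Study Drug Discontinuation visit", and that visit may itself be up to 5 days after last dose. Under Protocol 6 the visit window runs from 3 days before to "5 days from the nominal visit date for Week 4, Week 8, ATE Week 4" and the other visits in that list, which ends with EOS.

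**The concern.** Safety and tolerability is one of the two primary objectives (Protocol 2), and EOS is the off-drug safety check required of every subject. The schedule collects vital signs, ECG, chemistry, hematology, urinalysis and lipids at that visit. If the general data-period rule is programmed as written, none of these values reaches an overall summary, although two later SAP sections say that vital signs and ECGs will be carried to the end of study. A programmer has to break one rule to follow the other, and the SAP does not say which gives way.

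The same rule, taken literally, would also cut AEs at Day 5 after last dose, where SAP 3.7.2 counts them to Day 28. The two EOS anchors add a further uncertainty: how far AE collection can run past Day 28.

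**Working it through.** All days are counted after the last dose unless stated otherwise.

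**1. The plan's own figure.** The synopsis gives up to 69 weeks of participation: 5 + 12 + 48 + 4 = 69. Follow-up is therefore 4 × 7 = 28 days. Protocol 8.8.2 ends TEAEs at last dose plus the days in the follow-up period, so the SAP's 28 days reproduces the protocol rule.

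**2. EOS anchored to last dose** (window −3 to +5).
- Earliest: 28 − 3 = Day 25.
- Latest: 28 + 5 = Day 33.

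**3. EOS anchored to the discontinuation visit**, taken as 0 to 5 days after last dose. The protocol adds that this timing applies if possible, so 5 days is an assumption about compliant visits.
- Earliest: 28 + 0 − 3 = Day 25.
- Latest: 28 + 5 + 5 = Day 38.

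**4. Against the + 5-day limit.** The earliest compliant EOS under either anchor is Day 25, which is 25 − 5 = 20 days past the limit. No compliant EOS visit falls inside it.

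**5. Against the visit windows.** For a completer, the earliest ATE Week 48 visit is ATE Day 336 − 3 = 333, so the earliest EOS is ATE Day 333 + 25 = 358. The last window closes at ATE Day 350, so that EOS visit is labelled unscheduled. For an early discontinuer the EOS day can land inside another visit's window. With last dose on Induction Day 56, nominal EOS is Day 56 + 28 = 84, inside the Week 12 window (Days 77 to 98). Only the + 5-day limit (here Day 61) now stops it being read as a Week 12 value.

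**6. Against the 28-day TEAE rule.** Applied to AEs, the + 5-day limit would remove 28 − 5 = 23 days that SAP 3.7.2 includes. With the 28-day rule governing, the AE time collected but not tabulated is at most 33 − 28 = 5 days (last-dose anchor) or 38 − 28 = 10 days (discontinuation-visit anchor).

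**The case against.** **The specific sections may govern.** SAP 3.7.3.2 and 3.7.3.3 can be read as exceptions to the general rule, and the end of study in the ECG text might mean the last on-treatment visit. This stands in part: EOS vital signs and ECGs are ambiguous rather than certainly missing. But the vital-signs text sets the end of study apart from the visits, and laboratory data have no such sentence to rescue them. Listings also remain: SAP 3.1 lists all scheduled and unscheduled data, and 3.7.3.1 lists abnormal laboratory values.

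**The anchor conflict is small.** With the discontinuation visit on Days 0 to 5, the second anchor's nominal EOS is Day 28 to 33, inside the first anchor's window of Day 25 to 33. Day 38 needs both allowances at their extreme. Protocol 6.3.15 repeats the paragraph without the four-week phrase. The conflict is still in the text.

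**A reader might infer that most EOS visits fall after the TEAE cut-off.** Of the allowed days, 5 of 9 (56%) are after Day 28 under the last-dose anchor, and 44 of 54 day combinations (81%) under the other, which concerns early discontinuers only. These are shares of calendar days. The documents give no distribution of visit days, and the nominal Day 28 is inside the cut-off. Suppose a share p of visits falls on Day 28 and the rest spread evenly over the other 8 days. Under the last-dose anchor the share after Day 28 is then (1 − p) × 5/8: 50% at p = 0.20, 31% at 0.50 and 12.5% at 0.80.

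**A reader might also infer that events around the EOS visit disappear from every AE table.** The SAP classifies by onset date, so an AE starting on Day 27 and reported on Day 33 is kept. Only onsets after Day 28 leave the TEAE tables, and they are still listed. The AESI summary in SAP 3.7.2.1 and the line for deaths during study do not restate the TEAE limit, although the TEAE-only sentence in 3.7.2 is general.

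**The 28-day rule is defensible.** It follows the protocol. Protocol 1.4 equates 7 days with about 5 half-lives, so 28 days is about 28/7 × 5 = 20. Ending the window at the actual EOS date instead would make each subject's risk period depend on when the visit was booked.

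**The placebo-controlled comparison is little affected.** Induction TEAEs stop at the ATE Day 1 dose, and subjects who enter ATE reach EOS only after receiving TD-1473. Only those who stop during Induction have an EOS visit that bears on the comparison with placebo.

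**Conclusion.** The concern holds as an inconsistency within the SAP, plus a separate one in the protocol. Read literally, SAP 3.1.5.3 excludes every compliant EOS visit from the overall laboratory, vital-sign and ECG summaries, by at least 20 days, and the window table gives the visit no place. This contradicts SAP 3.7.3.2 and 3.7.3.3. For laboratory data there is a gap but no broken explicit promise. The + 5-day limit and the 28-day TEAE rule cannot both apply to AEs.

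The protocol's two EOS anchors disagree for early discontinuers. Their practical effect is bounded: at most 5 or 10 days of AE onset time is listed but not tabulated, if visits keep to their windows and the discontinuation visit takes place within 5 days of last dose. The documents do not support a claim about the proportion of visits or events affected, and the 28-day cut-off is not itself an error.

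**What to change.** - **SAP 3.1.5.3**, with matching words in 3.1.5.1 and 3.1.5.2: state that the + 5-day limit does not apply to AEs, for which SAP 3.7.2 governs, or to safety assessments at the EOS visit.
- **SAP 3.1.3**: add EOS to the visit windows, identified as its own visit, so that an early discontinuer's off-drug values are not assigned to a later on-treatment visit.
- **SAP 3.7.3.1 to 3.7.3.3**: show EOS laboratory, vital-sign and ECG values in a separate row labelled End of Study (off drug).
- **SAP 3.7.2**: keep the 28-day TEAE cut-off and the non-TEAE listing.
- **Protocol**: reconcile the early-discontinuation paragraph of 3.1 with the EOS paragraph of 3.1, with 6.3.10 and 6.3.14, and with footnote B in SAP 1.4. Which anchor applies is for the sponsor to settle.

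The cost is wording and one extra display row. No new data are needed.
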